In summary, the present pilot study aims to assess the feasibility and safety of an exercise programme in MGUS and SMM, and to provide preliminary data on disease activity, fitness and wellbeing outcomes for sample size calculations in a larger randomised controlled trial (RCT). Additionally, as part of this pilot study, a PhD project will investigate the potential mechanisms involved in possible changes in disease activity. Pilot data will allow a future larger randomised controlled trial to be designed optimally and to be adequately powered to assess the effect of exercise on disease activity, mechanisms and global fitness and wellbeing outcomes in MGUS and SMM. The unique clinical model proposed herein is anticipated to improve our wider understanding of how physical activity is linked to reduced cancer risk.

Aims and outcomes

The present trial will investigate the feasibility and safety of a 16-week progressive, walking-based exercise programme for MGUS and SMM.

Primary objectives and outcomes, measured throughout the trial period:

- Uptake (proportion of people approached who attend screening, proportion of people who attend screening that are deemed eligible)
- Adherence (proportion of supervised and home-based exercise sessions prescribed that are actually completed)
- Compliance (prescribed vs. actual aerobic exercise completed per supervised/home-based session)
- Retention (the proportion of participants who complete baselines measures that also complete follow-up measures)
- Safety (incidence and severity of adverse events)

Secondary objectives and outcomes, measured pre- and post-trial period:

- Disease activity of MGUS and SMM (M-protein, serum free light chains, beta-2 microglobulin)
- Physical fitness (VO_{2MAX}, balance, flexibility, strength)
- Free-living physical activity (e.g. duration, intensity, frequency, energy expenditure) and sedentary time (also measured during 8-month follow-up)
- Body composition (height, weight, waist and hip circumference, fat mass, lean mass, sagittal abdominal diameter)
- Wellbeing indices (frailty, fatigue, sleep, quality of life)
- CRAB indices (e.g. calcium; renal function [creatinine, estimated glomerular filtration rate; eGFR]; anaemia [full blood count, haemoglobin]; bone health [bone mineral density, bone mineral content, bone turnover biomarkers])
- Resting blood pressure and heart rate

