Participants will complete a Session Record Card in each supervised session. Home-exercise will be monitored using a Home Exercise Diary which will be reviewed each week. Participants will also be provided with a fitness tracker (Polar A370 wrist-worn device) for the duration of the trial period to record all training sessions. Data from the tracker will be downloaded by the researcher once a week, and the tracker will be returned after Visit 4.

The primary outcome of feasibility refers to the overall viability of the exercise intervention (e.g. how well can we recruit, can we keep participants engaged, are participants able to achieve the exercise intensities required) and the safety (e.g. do adverse events occur and are they unexpected and related to the trial treatment):

Uptake: Proportion of people approached who attend screening (recruitment rate) and the proportion of people who attend screening that are deemed eligible (screen-pass rate). Demographic characteristics will be compared across those who a recruited and those who decline to participate.

Adherence: Number of supervised and home-exercise sessions completed measured using a Session Record Card, Home Exercise Diary and Polar A370.

Compliance: Prescribed vs. actual aerobic exercise completed in each supervised session will be measured using the Polar A370 and chest strap HR monitor. Compliance to home-based aerobic exercise will be measured using the Polar A370.

Retention: Proportion of participants who complete baselines measures (i.e. Visit 1 and 2) that also complete followup measures (i.e. Visit 3 and 4).

Safety: Incidence and severity of adverse events (Table 1). [Recording and reporting of SAEs will follow University of Bath policy – The chief investigator (CI) should report any SAE to the sponsor within 24 hours. A written SAE report (health research authority [HRA] form) should be made by the lead researcher and sent to the CI who will assess the seriousness, causality and expectedness. Where the SAE is related and unexpected, the CI will notify the research ethics committee (REC) within 15 days of receiving the report. AEs and SAEs will be discussed by the trial management group.]

Table 1. Definitions of a	Table 1. Definitions of adverse events						
Term	Definition						
Adverse Event (AE)	Any untoward medical occurrence in a participant to whom an intervention has been administered, including occurrences which are not necessarily caused by or related to that product.						

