A home-based session has been included to increase exercise frequency without the additional burden of visits on participant's time and research feasibility. Home-based sessions are also being evaluated for potential use in a future, larger randomised-controlled trial. Walking exercise has been selected as this is an intervention that is accessible to the majority of people with MGUS and SMM.

Supervised exercise sessions

Supervised exercise sessions will be performed in the physiotherapy gym at the Royal United Hospital Bath. Each session lasts approximately 1 hour, and equipment needed for all exercises is available in the physiotherapy gym, including resistance bands and treadmills. A brief screening, including blood pressure measurement and review of health status, will take place before each supervised session to determine safety to exercise (unsafe if: blood pressure >200/120 mmHg (Ats and Accp, 2003) or participant reports new symptoms).

Exercise sessions will be offered at various times throughout the day so the programme is accessible to as many participants as possible, including those with diverse/busy routines (e.g. working / retired). Each exercise class has a maximum capacity of five participants per session. There will be drop-in sessions available for participants who have not been able to attend their scheduled exercise sessions.

Aerobic component

Participants will perform a warm up on the treadmill at a comfortable walking speed and 0% incline ('unloaded walking') for a minimum of 5 minutes. Aerobic training will then commence for 30 minutes. Participants will perform

three sets of 10-minute walking intervals (Table 2). For each interval, the gradient is increased during the 'work phase' to achieve a target HR (8 minutes, 40-80% VO_{2MAX}) followed by 'unloaded walking' (2 minutes). Target HR will be prescribed and monitored using HR data measured during CPET; participants will be given a HR zone that corresponds to the target percentage of VO_{2MAX}. An RPE guide (Borg 6-20 scale) will be used for people who present with a blunted HR response during CPET (e.g. medicated with beta blockers) as their HR response will be too small to differentiate zones that span a 10% change in VO_{2MAX}.

The Polar A370 will be worn with a chest strap HR monitor (Polar H10) during every supervised exercise session to prescribe intensity and record the session. The HR, RPE, speed and gradient will be recorded for each interval.

[figure not shown]

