Participants will perform two sets of 12-6 repetition maximum (RM) of six large muscle group exercises (reverse fly, chest fly, core twist, squat, calf raise, abduction) in line with resistance training guidance for people with a cancer diagnosis (Galvao et al., 2007). During a familiarisation session, the researcher will identify the colour of resistance band and grip rating that gives 12 RM for each exercise (e.g. level 1-5; diagram below) (Smith et al., 2017). This will be reassessed prior to each structured progression. To ensure continued progression, participants will be instructed to work past the prescribed RM and if they exceed the repetition target then additional resistance will be added prior to the next set/session by increasing grip rating or band colour (Cormie et al., 2013).

During familiarisation, the researcher will demonstrate each exercise and give feedback on a return demonstration performed by the participant. During subsequent sessions, circuit cards will be positioned around the physiotherapy gym to prompt correct technique and the researcher will be on-hand to provide assistance if needed. Participants will be asked to record the number of repetitions they perform, RPE, band colour and grip rating for each set in their session record card.

Version 3.1 19/DEC/18

Table 3. Resistance exercise prescription							
Trial week	Number of sets	Number of exercises	RM prescription				
1-2	2	6	15				
3-6	2	6	12				
7-10	2	6	10				
11-16	2	6	8				

Home-based exercise

Participants will be asked to complete one 40-minute walk each week at a moderate intensity (RPE 12-14) and daily balance and flexibility exercises (performed on days without a supervised session) which are detailed in the Home Exercise Pack. This increases the weekly aerobic exercise volume to 75-150 minutes at a moderate-vigorous intensity, and increases the frequency of balance and flexibility exercises, in line with WHO guidelines for physical activity in older adults.

Behaviour change

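### The compliance outcome names only heart-rate devices, although home-walk intensity, and supervised intensity in participants with a blunted heart-rate response, is prescribed by perceived exertion

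*Protocol*

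**What the plan says.** **Definition.** Protocol, Aims and outcomes, lists compliance among the primary outcomes and defines it as prescribed against actual aerobic exercise, session by session, for both supervised and home sessions. Trial period measurements adds that feasibility includes whether participants can reach the intended intensities.

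**Instruments.** Under Compliance in Trial period measurements, the supervised rule is "Prescribed vs. actual aerobic exercise completed in each supervised session will be measured using the Polar A370 and chest strap HR monitor". The home rule is "Compliance to home-based aerobic exercise will be measured using the Polar A370". The Adherence entry just above it draws on the Session Record Card, the Home Exercise Diary and the tracker. The Compliance entry names devices only.

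**Home prescription.** Home-based exercise states "Participants will be asked to complete one 40-minute walk each week at a moderate intensity (RPE 12-14"). It gives no heart-rate zone.

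**Supervised prescription.** Under Aerobic component, the default target is a heart-rate zone derived from the cardiopulmonary exercise test (CPET). There is one exception: "An RPE guide (Borg 6-20 scale) will be used for people who present with a blunted HR response during CPET", for example people on beta blockers. The reason given is that "their HR response will be too small to differentiate zones". The same section says that heart rate, RPE, speed and gradient are all recorded for each supervised interval, and Table 2 gives an RPE band for every training phase.

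**The concern.** A compliance measure has to be on the same scale as the prescription. The home walk has two prescribed parts, duration and perceived exertion. A tracker that records time and heart rate measures the first but not the second. For blunted-response participants the protocol goes further: it says that heart rate cannot separate the training zones, and then names heart-rate devices as the measure of whether those zones were reached.

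At stake is one of the five primary outcomes. Reaching the required intensity is part of the feasibility question, and Trial treatment says that home sessions are being evaluated for use in a later randomised trial. Followed as written, the plan leaves home compliance as either duration alone or a heart-rate threshold that the protocol does not state. An RPE that was never asked for at home cannot be recovered at analysis.

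**Working it through.** **Inputs**
- Sessions: two supervised and one home per week for 16 weeks (Trial summary; Trial treatment).
- Supervised aerobic block: 30 minutes, made of three 8-minute work phases and three 2-minute rests (Table 2). Home walk: 40 minutes (Home-based exercise).
- Planned sample: 20 (Sample size).
- Number of participants with a blunted heart-rate response: not stated. Beta-blocker use is not an exclusion, so an assumed range of 0 to 5 is shown.
- Assumption: the tracker provides session time and heart rate. The protocol says that it records all training sessions but does not list its variables.

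**1. The plan's own figure.** Supervised sessions = 2 × 16 = 32, which matches the 32 stated under Benefits of participating.

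**2. Share of home walks.** Home sessions = 1 × 16 = 16. Total = 32 + 16 = 48. Share = 16/48 = 33.3%. With 20 participants, 20 × 16 = 320 of 20 × 48 = 960 planned sessions. By time, home walks are 40 of 2 × 30 + 40 = 100 weekly aerobic minutes (40%), or 40 of 2 × 24 + 40 = 88 (45.5%) if only supervised work phases are counted.

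**3. Prescription against named instrument**

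| Component | Prescribed as | Compliance instrument named | Match |
|---|---|---|---|
| Supervised duration | 30 minutes | Tracker and chest strap | Yes |
| Supervised intensity, normal heart-rate response | Heart-rate zone | Tracker and chest strap | Yes |
| Supervised intensity, blunted response | RPE | Tracker and chest strap | No, but interval RPE is recorded |
| Home duration | 40 minutes | Tracker | Yes |
| Home intensity | RPE 12-14 | Tracker | No, and no home RPE record is described |

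**4. Sessions with an intensity mismatch under the literal definition.** With b blunted-response participants among 20, share = (20 × 16 + 32b)/960.

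| b (assumed) | 0 | 1 | 2 | 3 | 4 | 5 |
|---|---|---|---|---|---|---|
| Share | 33.3% | 36.7% | 40.0% | 43.3% | 46.7% | 50.0% |

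If the recorded interval RPE is used for these participants, the share is 320/960 = 33.3% whatever b is. What remains is home-walk intensity.

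**5. Can home RPE be converted to heart rate through Table 2?** The bands share endpoints: RPE 12-13 is paired with 40-50% of maximal oxygen uptake, 13-14 with 50-60%, and 14-15 with 60-70%. RPE 12-14 covers the first two rows (40-60%), but RPE 14 also opens the third. The conversion is therefore not unique. It is not stated for home walks, and it would not work in blunted-response participants.

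**The case against.** The strongest reply is that little or nothing is lost. Supervised RPE is recorded for every interval and Table 2 supplies the target, so supervised sessions of blunted-response participants can be scored once the definition says so. The tracker can check the 40 minutes at home. For participants with a normal heart-rate response, an individual heart-rate band could be built from the CPET, where RPE is recorded at each stage, and a statistical analysis plan that is not shown might define it. The Home Exercise Diary is reviewed weekly and its fields are not described, so it may already ask for RPE. Preferring device data to self-report at home is also defensible.

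Most of this stands, and it sets the limits of the point. A reader might infer that a third of all sessions, or all 48 sessions of a blunted-response participant, cannot be scored against prescription. The protocol does not support that: duration can be scored throughout, and supervised RPE exists. A reader might also infer that people on beta blockers would be misclassified. The protocol sets no threshold for compliant against non-compliant and reports feasibility as proportions, so there is no classification to get wrong.

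Two things survive the reply. The stated instrument differs from the stated prescription, which is more than a detail left for later. And an analysis plan can choose a conversion, but it cannot supply a home RPE that was not collected. If the diary does hold one, the compliance definition still does not use it.

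**Conclusion.** The point holds in a limited form. The compliance definition relies on heart-rate devices for two components prescribed by RPE:

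- **Home-walk intensity:** 16 of 48 sessions per participant (33%; 320 of 960 at the planned sample). No matching measure is named.
- **Supervised intensity in blunted-response participants:** up to 32 sessions each, number of participants unknown. The definition scores them with a signal that the protocol itself calls inadequate, while the right data are already being recorded.

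These counts are sessions in which one of two components lacks a matching named measure; they are not sessions lost. The conclusion rests on the tracker giving time and heart rate but not RPE, and on the compliance text being read as written. Whether the home diary already has an RPE field cannot be settled from the protocol. The amendment is worth making because this is a primary outcome and any missing home RPE has to be collected prospectively.

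**What to change.** Amend the Compliance entry under Trial period measurements as follows:

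1. **Supervised, heart-rate-guided participants:** keep chest-strap heart rate against the prescribed zone.
2. **Supervised, RPE-guided participants:** score intensity from the interval RPE already recorded, against the RPE column of Table 2.
3. **Home walks:** score duration from the tracker, and intensity from an RPE entry in the Home Exercise Diary against the RPE prescribed. Add the field if the diary lacks it.
4. **Reporting:** give duration and intensity compliance separately, for supervised and for home sessions. No joint pass/fail rule is needed, and 20 participants need not be divided into further groups.

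The cost is a few sentences of outcome wording and at most one diary field. Supervised data collection does not change. The drawback is that home RPE is self-reported; tracker heart rate can be shown beside it as supporting information for participants with a normal response. No prescribed intensity changes.

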- Unable to understand explanations and/or provide informed consent
- Any condition and/or behaviour that would pose undue personal risk or introduce bias into the trial

Trial procedures

Recruitment

The Royal United Hospital Bath maintains an active database of people who are routinely monitored for MGUS and SMM, diagnosed by International Myeloma Working Group (IMWG) criteria (Rajkumar et al., 2014). Suitable candidates will be posted an invitation letter and participant information sheet, and will receive a follow up telephone call 5-7 days later from a member of the healthcare team to discuss the trial and gauge interest in participating.

Those who are interested will be asked preliminary screening questions with the aim of minimising the number of unnecessary visits for people who will be deemed ineligible at a later stage. People will then be invited to attend a screening visit in the outpatient haematology clinic (zone A12, Royal United Hospital Bath).

As part of routine care, people with MGUS and SMM are regularly contacted by the healthcare team via telephone and post (e.g. to update on clinic appointments, to discuss results from regular disease monitoring tests, and to make contact about relevant patient events such as Myeloma UK meetings). Therefore, this recruitment method is deemed suitable by the healthcare team as it is familiar and reflects usual communication practice. Consent to use personal data (e.g. address / telephone number / medical history / age) is not being collected prior to screening as only members of the healthcare team will access this information, and at this stage this information is being used solely to identify people who are potentially eligible to participate and to advertise the trial.

Screening

Telephone screening questions were developed by the researcher and haematologist with the aim of reducing the number of unnecessary face-to-face screening visits. The criteria checked during telephone screening are simple self-report questions:

- WHO performance status
- Pregnancy
- PARQ (a brief questionnaire that is standard to complete in exercise settings, e.g. when joining a gym. It covers aspects of medical status that are used to determine a person's safety to exercise. People who give positive responses (answering 'yes') will require clearance to participate from the haematologist during face-to-face screening).

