Exclusion criteria that require the clinical judgement of the haematologist will only be addressed in face-to-face screening visits:

- Any comorbidity that is likely to progress or be exacerbated over the course of the trial period
- Cognitive impairment deemed a risk by the healthcare team for participation in the trial (e.g. diagnosis of neurodegenerative disease)
- Unable to understand explanations and/or provide informed consent
- Any condition and/or behaviour that would pose undue personal risk or introduce bias into the trial

Disease activity history, comorbidities and concomitant medications will be accessed from medical records by the researcher for reporting of eligibility after informed consent has been obtained.

Pre-screening procedures for the cardiopulmonary exercise test (Visit 2, page 14) will be performed at the screening visit. This includes resting electrocardiogram (ECG) and blood pressure. The ECG will be reviewed by [name] (Consultant Cardiologist, Royal United Hospital Bath) to identify risks that preclude cardiopulmonary exercise testing and ensure timely referral of participants for further assessment and intervention as needed. Anonymised ECG traces will be sent to [name] via NHS mail.

Consent

Written informed consent will be taken during the screening visit once patient eligibility has been confirmed and any questions about the trial have been answered. The haematologist will take informed consent.

People who elect not to participate during the initial telephone call, 5-7 days after receiving the recruitment material, will be asked during their next routine clinic appointment if they are willing to provide written informed consent to share their demographic data. This will be reported cross-sectionally at one time point to characterise people that decide not to take part for the primary trial outcomes, and will inform future design (e.g. recruitment strategies) of a larger RCT in this patient group.

Trial assessments

The trial comprises four measurement visits; two baseline visits (1 & 2) prior to the 16-week trial period, and two follow-up visits (3 & 4) following the 16-week trial period. Visits 1 & 3 take place in the Disability in Sport and Health Version 3.1 19/DEC/18

laboratory at the University of Bath, and Visits 2 & 4 take place in the Cancer Research Suite at the Royal United Hospital Bath. Measurements will also be taken throughout the 16-week trial period to address the primary outcomes.

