Strength: Upper-body strength will be reported as the average of three repetitions of a maximal grip strength test (kg) on each hand. Performance in a 30s chair stand test will be reported as the time (s) to complete five repetitions (strength) and the total number of repetitions completed (strength endurance) from a chair with a straight back and no arms.

Flexibility: Upper-body flexibility will be reported for left and right arms as the average distance (cm) between extended middle fingers in a back scratch test performed three times. Lower-body flexibility will be reported for left and right legs as the average distance (cm) between extended middle finger and the tip of the same-side toes in a chair sit-and-reach test performed three times.

Cardiorespiratory fitness

Maximal oxygen uptake (VO_{2MAX}) will be determined using a progressive incline cardiopulmonary exercise test (CPET) to volitional fatigue on a treadmill. Blood pressure and 12-lead electrocardiogram (ECG) will be recorded at rest. Treadmill speed will be kept constant, and after a 5-minute warm up at 0%, the gradient will increase by 3% every 3 minutes until fatigue (Thompson et al., 2010). Breath-by-breath gas exchange, ECG, blood pressure and oxygen saturation will be monitored continuously. A rating of perceived exertion (RPE) will be recorded at the end of each stage. A maximal effort will be verified by meeting two of four criteria: 1) heart rate (HR) within 10 bpm of age-

predicted maximum [220 – age (years)], respiratory exchange ratio \geq 1.00, RPE \geq 19 or an increment in VO₂ \leq 5 mL.kg⁻¹.min⁻¹ in response to increased gradient.

Participants unable to comply with the exercise test, for example due to a health problem raised during the exercise test (e.g. abnormal ECG or blood pressure response) or serious discomfort exercising, will discontinue involvement in the study on safety grounds. Abnormal test results will be referred to a cardiologist who will provide follow-up care and advice on the participants continued involvement in the trial. The decision on whether to repeat baseline measures will be discussed with the trial management group; e.g. if follow-up care results in a considerable delay, there may be a need to repeat baseline measures prior to commencing further trial activities.

Trial period measurements

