Serious Adverse Event	A serious adverse event in the context of this trial is any untoward medical occurrence						
(SAE)	 that: results in death is life-threatening requires inpatient hospitalisation or prolongation of existing hospitalisation results in persistent or significant disability/incapacity Other 'important medical events' may also be considered serious if they jeopardise the participant or require an intervention to prevent one of the above consequences. 						

NOTE: The term "life-threatening" in the definition of "serious" refers to an event in which
the participant was at risk of death at the time of the event; it does not refer to an event
which hypothetically might have caused death if it were more severe.

Follow-up measurements

Free-living measurements will be repeated post trial-period (week 17). Resources and equipment (i.e. an instruction pack, food diary, activity monitor and a sterile urine sample tube) to complete these measures will be given to participants in their final exercise session.

After the trial period, participants will repeat baseline visits. Measurements conducted during Visit 3 will replicate Visit 1, and measurements conducted during Visit 4 will replicate Visit 2, as described above.

Participants will answer a physical activity questionnaire (IPAQ short-form) via telephone interview at time-points which coincide with routine disease monitoring during the 8 months following visit 4.

Withdrawal criteria

Participants may be withdrawn from the trial if there is a change in their eligibility e.g. disease progression to symptomatic multiple myeloma. During visit 2, contraindications and limitations to exercise may be identified during the CPET (Ats and Accp, 2003) which will result in participants being withdrawn on safety grounds. All withdrawals will be discussed with the haematologist and reported in primary outcomes (retention).

Storage of clinical samples

Samples will be collected and processed in a laboratory at the University of Bath:

- 15 mL into serum vacutainers, from which serum will be extracted and stored in multiple aliquots at -80°C for later analysis (e.g. disease activity, immune competence, inflammation, hormones and metabolic factors).
- 25 mL into a heparin-treated syringe, from which peripheral blood mononuclear cells (PBMCs) will be isolated by density gradient centrifugation and stored at −140 to −150°C for later analysis (e.g. phenotypic and functional measures of immune competence).

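### The retention ratio counts only participants who complete Visits 1 and 2, yet the protocol says withdrawals at the Visit 2 exercise test are reported in retention; those stopped before Visit 2 is complete drop out of the ratio.

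*Protocol*

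**What the plan says.** Retention is one of the primary outcomes. Aims and outcomes defines it among participants who complete the baseline measures. Trial period measurements repeats this and names the visits: "Proportion of participants who complete baselines measures (i.e. Visit 1 and 2) that also complete followup measures (i.e. Visit 3 and 4").

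The CPET belongs to Visit 2. Under Cardiorespiratory fitness, participants who cannot comply with it "will discontinue involvement in the study on safety grounds". The same paragraph leaves a way back: "Abnormal test results will be referred to a cardiologist who will provide follow-up care and advice on the participants continued involvement in the trial", and baseline measures may be repeated after a long delay.

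Withdrawal criteria says that contraindications and limitations may be found during the Visit 2 CPET, "which will result in participants being withdrawn on safety grounds". It continues: "All withdrawals will be discussed with the haematologist and reported in primary outcomes (retention").

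Consent comes before all of this: "Written informed consent will be taken during the screening visit once patient eligibility has been confirmed". The Statistical analysis plan section says that feasibility, including retention, will be reported as proportions.

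**The concern.** The definition and the reporting rule give different answers for the same person. A participant who has passed screening and consented, and is then stopped during the CPET, has not completed Visit 2. The definition leaves that person out of the ratio altogether; Withdrawal criteria says the withdrawal is reported there.

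The error runs one way. Removing losses from the denominator can only raise the proportion, and the people removed are safety withdrawals in a trial whose primary question is feasibility and safety. They have already counted as eligible in the screen-pass rate. The safety outcome will not necessarily show them either, because a contraindication found on testing need not be an adverse event.

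The primary outcomes are descriptive proportions, so the choice of denominator is the analysis, and the protocol itself fixes it. A future randomised trial planned on this figure would allow for too little loss between consent and follow-up.

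**Working it through.** **Inputs from the protocol**
- Target of 20 participants and 15% drop-out (Sample size). The denominator of the 15% is not stated.
- Retention as defined: completed Visits 3 and 4 ÷ completed Visits 1 and 2 (Trial period measurements).
- Withdrawals at the CPET are part of retention (Withdrawal criteria).

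The protocol derives no retention figure, so there is none to reproduce. The one consistency check is 20 × (1 − 0.15) = 17 completers, that is, 3 losses.

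**Assumptions**
- All 20 consent, and 17 complete Visits 3 and 4.
- Of the 3 losses, k occur before Visit 2 is complete. The protocol gives no expected value for k, so the full range 0 to 3 is shown.

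**Formulas**, with N consented and C completers:
- retention from consent = C / N
- retention as defined = C / (N − k)
- overstatement = C / (N − k) − C / N

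**Results** (exact Clopper-Pearson 95% intervals)

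| k | As defined | From consent | Difference |
|---|---|---|---|
| 0 | 17/20 = 85.0% (62.1 to 96.8) | 17/20 = 85.0% (62.1 to 96.8) | 0 |
| 1 | 17/19 = 89.5% (66.9 to 98.7) | 17/20 = 85.0% | 4.5 points |
| 2 | 17/18 = 94.4% (72.7 to 99.9) | 17/20 = 85.0% | 9.4 points |
| 3 | 17/17 = 100% (80.5 to 100) | 17/20 = 85.0% | 15.0 points |

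**Sensitivity to the meaning of 15%.** Suppose instead that 3 people leave after baseline and the k losses come on top:
- k = 1: 16/19 = 84.2% against 16/20 = 80.0%, a difference of 4.2 points.
- k = 2: 15/18 = 83.3% against 15/20 = 75.0%, a difference of 8.3 points.

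The overstatement for a given k is similar on either reading.

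**Dependence on what counts as completing Visit 2.** With one CPET withdrawal among the 3 losses, retention is 89.5% if that person is held not to have completed Visit 2, and 17/20 = 85.0% if held to have completed it. The protocol does not say which applies to someone who finishes the test and is withdrawn on its result.

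**The case against.** **The baseline-completer denominator is a legitimate choice.** Risks of participating lists the exercise ECG among the checks at trial entry, so the CPET works partly as a safety gate before the programme starts. Retention among those who pass it answers whether participants stay engaged, and a consent denominator mixes entry-test exclusions with attrition. This stands as a reason to keep the existing ratio. It does not remove the conflict with Withdrawal criteria, which places these withdrawals in retention.

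**Listing the withdrawals beside the proportion would satisfy Withdrawal criteria.** It would, and the fix below uses this. The current definition makes no provision for such a list.

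**The shift is small beside the imprecision.** The interval for 17/20 runs from 62.1% to 96.8%, and no retention threshold is set, so no stated decision changes. This is correct and limits the consequence. The shift is still systematic and favourable, which sampling error is not.

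**Stronger readings that the protocol does not support**
- A reader might infer that no CPET withdrawal can enter the ratio. Someone who finishes the test and is then withdrawn can count as having completed Visit 2, and cardiology advice may lead to continuation or a repeated baseline. Only those stopped before Visit 2 is complete are affected.
- A reader might put the overstatement at 16 points, from 13/16 = 81.3% against 13/20 = 65.0%. That needs 4 of 20 stopped at the CPET in addition to 3 later losses, and nothing in the protocol suggests such a number.
- A reader might infer that the uptake rates are distorted in the same way, because telephone screening is done "with the aim of minimising the number of unnecessary visits for people who will be deemed ineligible at a later stage". The uptake rates are "Proportion of people approached who attend screening (recruitment rate) and the proportion of people who attend screening that are deemed eligible (screen-pass rate"). Telephone-ineligible people remain in the denominator of the first rate, and the second is openly defined on attenders. The product of the two, eligible over approached, is unaffected. Consent and Trial period measurements both treat decliners as a group of their own. The telephone questions are few, and a positive readiness questionnaire is passed to the visit for clearance.

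**Conclusion.** The point holds for retention only. Aims and outcomes and Trial period measurements limit the ratio to baseline completers; Withdrawal criteria says it takes in all withdrawals, expressly including those arising at the Visit 2 CPET. Both cannot be true for a consented participant stopped before Visit 2 is complete, and the ratio as written overstates retention for each such person.

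If 20 consent and 17 finish, the overstatement is 4.5, 9.4 or 15.0 points for 1, 2 or 3 such losses, and nil if there are none. The 20 and the 15% are the protocol's own figures; reading them as 20 consented and 17 finishing, and the number lost before completed baseline, are assumptions. This is an error in the definition of a reported primary figure. It does not affect the uptake rates.

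**What to change.** Reconcile Aims and outcomes, Trial period measurements and Withdrawal criteria as follows.

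1. Report retention as participants completing Visits 3 and 4 divided by all who gave consent.
2. Keep the baseline-completer ratio beside it, labelled as such, and say what counts as completing Visit 2 when the test is finished but the participant is then withdrawn on its result.
3. Count and list losses before completed baseline, with Visit 2 CPET withdrawals shown separately, apart from losses during the programme. Classify a participant who returns after cardiology advice by final status.
4. If wanted, show telephone-ineligible people and decliners as separate counts in the participant flow. The uptake definitions need no change.

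The statements on discontinuing and on possible continuation after the CPET should be read together when the wording is settled; no clinical stopping rule is proposed here.

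The cost is wording and a short tally of participants by stage. No visit, procedure or sample size changes. The headline retention figure may be slightly less favourable.
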